Threat of shock is a well-validated ([name] and Ameli, 1998; Lang et al., 1990), translational procedure ([name], 2008a; [name] et al., 1994; Morgan et al., 1995; Robinson et al., 2012b), previously shown to increase state anxiety (Dunning et al., 2013; Hansen et al., 2009; Robinson et al., 2013b; Vytal et al., 2014), cause worry ([name], 2002, 2008b), and interfere with task performance (Balderston et al., 2015; Clarke and Johnstone, 2013; Lavric et al., 2003; Robinson et al., 2011, 2013a). In a typical threat of shock experiment, subjects are exposed to alternating blocks in which they are safe, or at risk for receiving an unpleasant electrical stimulation. Because the shock can be delivered infrequently, it is possible to superimpose a wide variety of tasks onto these alternating blocks, with little interference from the actual shock presentations, making this paradigm ideal for experimentally testing the effects of anxiety on cognitive processes, and their underlying neural mechanisms.

It is clear from resting state studies that threat of shock changes patterns of functional connectivity even in the absence of a cognitive task (McMenamin et al., 2014; McMenamin and Pessoa, 2015; Robinson et al., 2012a), and our data suggest that these resting state changes may be most robust in parietal regions of the frontoparietal attention network (FPN), potentially reflecting a state of threat induced hypervigilance (Balderston et al., 2017). Therefore, successful performance of a task during this altered baseline state may require additional cognitive control, when compared to non-threat periods. One candidate region that may be involved in this implicit emotion regulation is the dorsolateral prefrontal cortex (dlPFC). Indeed, the dlPFC has been repeatedly shown to play a role in WM (Altamura et al., 2007; Barbey et al., 2013; Curtis and D’Esposito, 2003; Feredoes et al., 2011; Geier et al., 2007), anxiety (Bishop, 2009; Forster et al., 2015; Nitschke et al., 2006; Peers et al., 2013; Shang et al., 2014), and emotional learning

(Carter et al., 2006). Studies with high anxious healthy controls have also implicated the dlPFC in anxiety/task interactions (Basten et al., 2011, 2012; Bishop, 2009; Eysenck et al., 2007; Fales et al., 2008; Telzer et al., 2008). In our pilot work, we show that even low load tasks activate the dlPFC under threat of shock, but that this activity is increased as cognitive load is increased.

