4. Study Design and Methods

a. Study overview

Sub-studies 1 and 2 will consist of 2 outpatient visits (1 MRI visit, 1 TMS visit), each lasting up to 3 hours each. Sub-study 3 will consist of 3 outpatient visits (1 MRI visit, 2 TMS visits). Healthy volunteers will be assigned to one of the three sub-studies. All visits will be located in the Clinical Center at the NIH in Bethesda, MD. The MRI visit will take place in the NMR center and the TMS visits will take place on the 7th floor inpatient unit. The visits will be separated by ~1 week (no more than 2 weeks), according to the subject's availability. Each participant will sign the consent form during the MRI visit.

MRI visit. The MRI visit will be used to identify single-subject FPN targets for TMS. Subjects participating in multiple sub-studies will complete the MRI visit only when participating in their first sub-study, unless the MRI visit needs to be repeated. First subjects will complete the TMS Adult Safety Screen (TASS) (Keel et al., 2000), to ensure that they meet the inclusionary criteria for TMS. Only subjects eligible for TMS will complete the MRI visit. Subjects in Sub-study 3 will also receive TMS sensation screen. During this screen, subjects will receive a single train of electric scalp stimulation, and asked whether they would be willing to tolerate this level of scalp stimulation during the TMS sessions.

Next, subjects will be setup to go into the MRI scanner. A T1, a T2, and a diffusion weighted echo-planar series will be collected to assist with targeting (Fox, 2009). After, the subject will undergo 1 run of resting state, and 1 run of the Sternberg WM task without shock, to identify single-subject FPN targets for TMS. This visit will be the same for subjects in both sub-studies.

Sub-studies 1 and 2 TMS visit. During the TMS visits, subjects will first be prepped for the procedure. Shock, and physiology electrodes will be attached (See below for details). Subjects will undergo the shock workup and startle habituation procedures. Next subjects will undergo motor threshold testing to determine the proper TMS dose. Afterward the subjects will receive stimulation TMS while completing the task (WM or NPU). Stimulation type will be manipulated within subjects, across trials. Subjects will receive active or sham TMS to the left IPS during random intervals of the NPU task, or during a random selection of WM trials.

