During the TMS visit, the subject will complete a packet of pre-experiment questionnaires. Next the subject will be connected to the equipment. The stimulation device, as well as the electrodes for shock and autonomic measures will be attached, and the subject will be given headphones for the white noise delivery. Subjects will undergo TMS motor threshold testing (during first TMS visit only for sub-study 3). Once the subject is prepped for the experiment, they will undergo startle habituation, and the shock workup. After the shock workup, subjects will complete the task while receiving TMS. Once the task is complete, the subject will complete retrospective questionnaires. For sub-studies 1 and 2, each subject will be assigned to one of two tasks (Sternberg WM or NPU). The TMS visit will be the same for subjects in both sub-studies with the exception of being assigned to one of the two tasks. For sub-study 3, subjects will participate in the NPU task pre and post TMS delivery, which will occur during a run of the Sternberg WM task (for active TMS targeting).

Sub-study 1, Sternberg task: The session will begin with a startle habituation phase with 9 startle stimuli presented alone to reduce startle reactivity. On each WM trial, subjects will see a series of 4 letters presented singularly (encoding period) that will be followed by a brief interval where subjects are required to maintain these letters (maintenance period). At the end of the maintenance period, subjects will be prompted to make a response based on the task instructions (response period; Sternberg, 1966). The response prompt will consist of a letter and a number. The letter will be chosen from the study series, and the number will correspond to a position in the series. The subjects will indicate whether the position of the letter in the series matches the number.

There will be 4, 14 min runs of the experiment (2 active and 2 sham). Within each run, there will be 4 blocks (2 threat, 2 safe). During 1 block each of safe and threat, subjects

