will receive a continuous train of 1 Hz stimulation to the left IPS. Within each block, there will be 2 types of trials based on the delivery of startle probes. On each trial a startle probe will be presented either during the maintenance period or the ITI. There will be 6 trials per condition per block, resulting in a total of 192 trials across the entire experiment (2 [active vs. sham] x 2 [threat vs. safe] x 2 [maintenance vs. ITI] x 2 [TMS vs. no TMS] x 2 [run repetitions] x 2 [block repetitions] x 3 [trial repetitions]). Trials will last approximately 17 seconds. There will be a total of 3 shocks per run presented at random points during the threat blocks.

Sub-study 2, NPU Task: The instructed fear paradigm that will be implemented uses administration of predictable and unpredictable shocks to generate phasic and sustained forms of potentiated startle. We will use the NPU threat procedure as described in (Schmitz and [name], 2012). The experiment consists of three different conditions: no shock (N), predictable shock (P), and unpredictable shock (U), each lasting approximately 150 sec. In the N condition, no shocks will be delivered. In the P condition, shocks will be administered predictably, that is, only in the presence of a threat cue. In the U condition, the shocks will be unpredictable. In each 150-sec condition, an 8-sec cue will be presented four times. The cues will be different geometric colored shapes in each condition (e.g., a blue square for N, a red circle for P, and a green star for U) presented on a computer monitor in front of the subjects. The cue will signal the possibility of receiving a shock only in the P condition. It has no signal value in the N and U conditions. Instructions will also be displayed on a computer monitor to inform subjects of the nature of current condition by showing the following information throughout the testing procedure: “no shock” (N), “shock only during shape” (P), or “shock at any time” (U). During each predictable and unpredictable condition, one shock will be administered during the cue in the predictable condition and in the absence of a cue in the unpredictable condition.

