There will be 4, 14 min runs of the experiment (2 active and 2 sham). Within each run, there will be 8 blocks (2 predictable, 2 unpredictable, 4 neutral). There are twice the number of neutral blocks to ensure that safe blocks alternate with threat (predictable or unpredictable) blocks. During half of the blocks (1 predictable, 1 unpredictable, 2 neutral), subjects will receive a continuous train of 1 Hz stimulation to the left IPS. Within each block, there will be 2 types of trials based on the delivery of startle probes. Startle probes will be presented either during the cue period, or the ITI. During the predictable and unpredictable blocks, there will be 4 trials per condition. Given that there will be twice as many neutral blocks, during these blocks there will only be 1 trial per condition. The result will be a total of 192 trials across the entire experiment (2 [active vs. sham] x 2 [neutral vs. predictable vs. unpredictable] x 2 [maintenance vs. ITI] x 2 [TMS vs. no TMS] x 2 [run repetitions] x 4 [block*trial repetitions]). Trials will last approximately 17 seconds. There will be a total of 3 shocks per run presented during either the ITI (unpredictable) or cue (predictable) periods.

Sub-study 3, NPU task: There will be 1 pre-TMS and 1 post-TMS NPU run during each TMS visit. Within each run, there will be 8 blocks (2 predictable, 2 unpredictable, 4 neutral). There are twice the number of neutral blocks to ensure that safe blocks alternate

with threat (predictable or unpredictable) blocks. Startle probes will be presented either during the cue period, or the ITI. During the predictable and unpredictable blocks, there will be 2 trials per condition. Given that there will be twice as many neutral blocks, during these blocks there will only be 1 trial per condition. The result will be a total of 192 trials across the entire experiment (2 [active vs. sham] x 3 [neutral vs. predictable vs. unpredictable] x 2 [maintenance vs. ITI] x 2 [pre-TMS vs. post-TMS] x 8 [block*trial repetitions]). There will be a total of 3 shocks per run presented during either the ITI (unpredictable) or cue (predictable) periods.

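### Sub-study 2 gives two shock counts that cannot both be followed (4 or 2 per run by one rule, 3 by another); sub-study 1 could remove chance shock imbalance at almost no cost

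*Combined protocol and SAP*

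**What the plan says.** All of this is in section 4d (Study procedures) of the combined protocol and SAP.

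- **Sub-study 2, shock rule.** "During each predictable and unpredictable condition, one shock will be administered during the cue in the predictable condition", and the sentence goes on to place the shock outside the cue in the unpredictable condition. A condition here is a period of about 150 seconds; the neutral condition has no shocks.
- **Sub-study 2, layout.** There are four 14-minute runs, two active and two sham, each with 2 P, 2 U and 4 neutral blocks. "During half of the blocks (1 predictable, 1 unpredictable, 2 neutral), subjects will receive a continuous train of 1 Hz stimulation", so each run has one P and one U block with TMS and one of each without.
- **Sub-study 2, stated count.** "There will be a total of 3 shocks per run presented during either the ITI (unpredictable) or cue (predictable) periods".
- **Sub-study 3.** It has the same 2 P, 2 U and 4 neutral blocks per run and repeats the count of 3. It has no TMS/no-TMS blocks within a run.
- **Sub-study 1.** Each run has two threat and two safe blocks, with TMS in one of each. "There will be a total of 3 shocks per run presented at random points during the threat blocks".

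The analysis in section 10a crosses active/sham with TMS/no TMS in repeated measures ANOVAs, so shocks in TMS and no-TMS threat blocks fall into different cells.

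**The concern.** There are two separate matters.

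The first is a contradiction. The sub-study 2 rule and the sub-study 2 count describe different experiments, and nothing says which prevails. Whoever scripts the task must choose, and the choice changes both the number of aversive stimuli each subject receives and whether every threat block contains a shock.

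The second is an omission. With 3 shocks per run, TMS and no-TMS threat blocks cannot receive equal numbers within a run, and no text asks that they even out over the two runs of each stimulation type. The balance statements in section 1c concern the effect of scalp stimulation across conditions, not the placement of shocks. Shocks occur only in threat blocks, so the threat-minus-safe subtraction does not cancel any effect they have on startle. Such an effect would appear as within-subject noise in the TMS/no-TMS factor and in its interaction with active/sham.

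**Working it through.** **1. Can the stated count be reproduced?** Inputs: 2 P and 2 U blocks per run, 4 runs, one shock per P or U condition.

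| Reading | Shocks per run | Shocks per subject (x 4 runs) |
|---|---|---|
| One per P or U block | 2 + 2 = 4 | 16 |
| One per condition type per run | 1 + 1 = 2 | 8 |
| Count as stated | 3 | 12 |

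No reading of the rule gives 3. At 12, with at most one shock per block, 16 - 12 = 4 threat blocks have no shock, contrary to the per-block reading.

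**2. Which text is likely to be operative?** The layout paragraph gives 192 trials over 4 runs, or 48 per run. (Its printed product reaches 192 only with 3 rather than 2 levels for neutral/predictable/unpredictable.) "Trials will last approximately 17 seconds", so a run takes 48 x 17 s = 816 s = 13.6 min, which fits 14 minutes. Eight blocks of 150 s would take 1,200 s = 20 min, which does not. The layout paragraph is therefore probably the intended design, but this does not derive the figure of 3.

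**3. Balance in sub-study 1.** Three shocks over one TMS and one no-TMS threat block split 2:1 or 3:0. Assume that each shock falls independently, with equal chance, in either block. Then:

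- Within a run: 3:0 has probability 2/8 = 25%, and 2:1 has 6/8 = 75%.
- Over the two active runs, Binomial(6, 0.5): 3-3 is 20/64 = 31%; 4-2 is 30/64 = 47%; 5-1 or 6-0 is 14/64 = 22%. The same holds for the two sham runs.
- The TMS minus no-TMS difference in shocks has mean 0 and variance 6 (SD 2.45).

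**4. Balance in sub-study 2 at 3 per run.** Assume at most one shock per block and a skipped block chosen at random from the four.

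- In each run the U-TMS minus U-no-TMS difference is +1, 0 or -1 with probability 1/4, 1/2 and 1/4, so its variance is 0.5 per run and 1 over two runs.
- The U cells are equal within a given stimulation type with probability 1/4 + 1/8 = 37.5%.
- The active/sham by TMS/no-TMS contrast in U shocks is exactly balanced in 70 of 256 schedules (27.3%).
- Six shocks per stimulation type over four P/U by TMS/no-TMS cells is 1.5 per cell, so all four cannot be equal.

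**5. Size.** The documents give no figure for the effect of a shock on anxiety-potentiated startle (APS). Let b be the assumed shift in a cell's APS per extra shock, in SDs of the subject-level TMS minus no-TMS difference. The variance of that contrast within one stimulation type is multiplied by 1 + V x b², where V is the variance of the shock difference.

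| b (assumed) | Sub-study 1 (V = 6) | Sub-study 2 (V = 1) |
|---|---|---|
| 0 | 1.00 | 1.00 |
| 0.10 | 1.06 | 1.01 |

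At b = 0.10 this is worth 48 x (1 - 1/1.06) = 2.7 completers in sub-study 1 and 48 x (1 - 1/1.01) = 0.5 in sub-study 2.

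**The case against.** The best defence on the count is that the one-shock rule belongs to a description of the published NPU procedure, while the layout paragraph is this study's own design. The timing supports that, and the repetition of 3 for sub-study 3 suggests the number is deliberate. This makes 3 the likelier intention. It does not remove the conflict: the rule is written as what will be done in sub-study 2, and nothing says that the later count replaces it.

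On balance, the defence is stronger. Random placement is a legitimate method and suits an unpredictable threat. The study overview also places "active or sham TMS to the left IPS during random intervals of the NPU task, or during a random selection of WM trials". A protocol need not print the stimulus script, so silence does not show that the script is unconstrained.

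A reader might infer that uneven shocks bias the TMS comparison. The documents do not support that. Active and sham runs carry equal totals (6 and 6 at 3 per run), the expected TMS/no-TMS imbalance under random placement is zero, and section 1a says that tasks can be run under threat "with little interference from the actual shock presentations".

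A reader might also count the schedules in which all four U cells (active/sham by TMS/no-TMS) are identical: 20 of 256, or 7.8%. That is a stricter standard than the analysis needs; the 37.5% and 27.3% above are the relevant figures.

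**Conclusion.** The count conflict stands and rests on the text alone: 16, 8 or 12 shocks per subject in sub-study 2, with no rule for choosing. The balance point stands only as an inexpensive improvement in precision. In sub-study 1 an even split within a run is impossible. Under independent placement only 31% of subjects would be balanced over the active runs. This is chance imbalance within subjects, not bias. Removing it gains between 0% and about 6% of contrast variance in sub-study 1, and between 0% and about 1% in sub-study 2. Both upper limits depend on an assumed effect of 0.10 SD per extra shock that has no source in the documents. Severity: minor.

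**What to change.** **Sub-study 2.** State one count. The preferred choice is one shock in each threat block, 4 per run. This is already the written rule, and it gives 16/8 = 2 shocks in each P/U by active/sham by TMS/no-TMS cell. The cost is 4 more shocks per subject than 12, and a subject may come to expect no further shock once a block's shock has occurred. Random timing within the block limits this.

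If 3 per run is kept, constrain the skipped block so that TMS and no-TMS cells even out over the two runs of each stimulation type, and disclose any P/U difference. For example, 1 P + 2 U per run, with the P shock alternating between the TMS and no-TMS blocks, evens the cells. It also gives 4 P against 8 U shocks per subject and leaves one P block per run without a shock, so the one-shock-per-condition sentence would have to be reworded.

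**Sub-study 3.** Set its count in the same edit, or say why it differs.

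**Sub-study 1 (optional).** Keep 3 per run, but allocate 2+1 in one run and 1+2 in the other over the TMS and no-TMS threat blocks, for each stimulation type. Randomise the order of the two runs and keep timing within blocks random. Every subject is then 3-3 in active and in sham runs, with the total unchanged.

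The work is a change to the stimulus script and a few sentences of protocol text. It needs no extra subjects or visits.

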TMS: In 2008, the FDA approved the use of high frequency rTMS in the treatment of depression. In 2009, a safety guideline was published whereupon the authors systematically reviewed the thousands of healthy subjects and patients who have undergone rTMS in order to allow better assessment of relative risk (Rossi et al., 2009). The relative infrequency of adverse events using rTMS was noted include the rTMS intensity and timing parameters considered safe, training, and planning for and managing emergencies. We will follow these guidelines, and have incorporated them into our screening and session procedures.

Although there are no known long-term health risks to the use of TMS when operated within consensus safety guidelines (Rossi et al., 2009), the greatest potential short-term risk in the use of TMS is seizure. The Rossi et al. (2009) consensus safety report stated that "the occurrence of seizures has been extremely rare, with most of the few new cases

receiving TMS protocols exceeding previous guidelines, often in patients under treatment with drugs which potentially lowered the seizure threshold.” As Rossi et al. delineate, “rare” means that up to the end of 2008, 16 cases of seizure related to TMS had been reported, out of tens of thousands of TMS sessions over the last two decades. Seven occurred before safety parameters were established in 1997. These seizures appeared to be the result of excessive stimulator intensity, pulse frequency and train duration and too short inter-train intervals, in various combinations, and resulted in the establishment of safety guidelines for each parameter. Higher frequencies of TMS are most closely associated with seizure risk. While high frequency TMS will be employed in this protocol (5 Hz rTMS), the parameters to be used are well within suggested safety limits.

Aside from seizure, other adverse effects of TMS include headache, vasovagal syncope and hearing effects. Stimulation over superficial scalp tissue can result in headaches, typically of a muscle-tension type, and local muscle aches, especially with high-frequency TMS. They usually develop during or immediately after the stimulation, may last for minutes to hours following the end of the stimulation, and usually respond promptly to single doses of over the counter pain medications. Cramped conditions extended in time within frameless stereotaxic apparatus can also lead to head and body aches. Both are usually managed easily with over-the-counter analgesics. The sensation of the TMS pulses on the scalp can trigger vasovagal syncope (i.e. fainting) in some individuals, but these episodes typically resolve without the need for follow-up (Gillick et al., 2015; Kesar et al., 2016; Riedel et al., 2016). In addition, hearing loss and tinnitus may result from TMS. The clicking sound made by the TMS coil at high intensities may not sound extremely loud, but this is deceptive: subjective loudness is a function of both sound intensity and duration, and the duration of a TMS pulse is less than a millisecond. The sound intensity can be quite high, exceeding 100 dB and federally-recommended safety levels. It has been recommended that all participants wear ear protection with TMS exposure (Rossi et al., 2009).

MRI: MRI is widely regarded as a safe, noninvasive procedure for visualization of brain tissue. The risks involved with fMRI are the same as those involved in standard anatomic MRI, since these three procedures rely on the same physical properties of brain tissue. This study will be performed on an FDA approved 3T scanner at the NIMH. Potential risk of heart rhythm disturbances exists for patients with a history of heart rhythm abnormalities or those who have certain types of pacemakers. A substantial risk to persons who have metallic objects inside their bodies exists, as the magnet in the scanner can cause these to move. Pregnant women should not undergo MRI because of the possible harmful effects to the fetus.

MRI at 3 Tesla is a routine clinical procedure, and issues regarding radio frequency deposition, time varying magnetic fields, and the static field at 3 Tesla do not require detailed discussion. fMRI scanner is very noisy for this reason participants wear ear plugs, or headphones that are designed to reduce the noise impact of the scanner. The enclosed space of the scanner can be uncomfortable. Participants have access to a panic button at all times and can press this to stop the scan and be removed from the scanner.

b. Procedures to Minimize Risks

Electric Shock: Shock will be delivered at a level that is judged by the subject as uncomfortable but tolerable. Study shock levels will be determined before the test begins. The subject may stop the experiment at any time if they find the discomfort to be too great.

TMS: Seizure is a theoretical risk with rTMS. In the Rossi et al. report it was stated that: “The occurrence of seizures has been extremely rare, with most of the few new cases receiving rTMS protocols exceeding previous guidelines, often in patients under treatment with drugs which potentially lowered the seizure threshold.” As Rossi et al. delineate, “rare” means that 16 cases (out of tens of thousands of rTMS sessions over the last two decades) of seizure related to rTMS have been reported. Eight occurred before safety parameters were established in 1997. Of the other eight reports, six occurred either when the safe rTMS parameters were exceeded or other safety guidelines ignored, and the actual occurrence of a seizure has been questioned in the other two (i.e., convulsive syncope or pseudoseizure may have occurred). In a workshop convened by the National Institute for Neurological Disorders and Stroke (NINDS) in 1996 (including the PI here, [name], and one of the investigators, [name]), researchers in the field agreed upon a set of *rTMS consensus safety guidelines*, including recommended stimulation parameters and contra-indications (Wasserman, 1998), and these consensus guidelines have been updated (Rossi et al., 2009). Widespread adherence to the 1996 guidelines has resulted in the virtual elimination of inadvertent seizures in rTMS studies (Rossi et al., 2009). The levels of stimulation used in this protocol are well within safety guidelines (Rossi et al., 2009; Wasserman, 1998).

We will screen subjects for known risk factors for seizure with rTMS (using the TASS questionnaire) after consent during the MRI visit (Keel et al., 2000). Personnel who administer rTMS are trained to recognize a potential seizure event and to act as “first responders” in order to administer appropriate initial care. All study personnel have undergone first-aid and CPR training, and seizure-specific training. The major physical signs the study personnel will look out for in detecting a potential seizure include chewing movements, convulsions/tremor/shaking, difficulty talking, a blank stare, eyes rolling up, and profuse sweating. If any of these signs are observed, study personnel will stop the research procedure and inquire whether the subject feels okay. If the subject is unresponsive (and therefore likely experiencing a seizure), first-aid will be supplied. The first-aid response consists of making sure the subject is physically safe for the duration of the seizure. This involves moving the subjects out of the TMS chair and onto the floor lying down on his or her left side. The subject will be kept lying down on his or her left side, while the staff call a code blue, as per NIH Clinical Center policy. Resources available in the laboratory include a first-aid kit and immediate phone access. A seizure constitutes a reportable adverse event, and will thus be immediately reported to the IRB via the Safety Events Form mechanism.

The most commonly reported side effect of rTMS is headache. This headache is typically of a muscle-tension type. It usually develops during or immediately after the

stimulation and may last for minutes to hours following the end of the stimulation. It is typically limited to the day of stimulation, and usually responds promptly to single doses of over the counter pain medications. Neck pain or scalp pain may also occur. This is especially true for TMS to frontal regions. For this we may offer a topical lidocaine cream to reduce the scalp pain for sub-study 3 which employs frontal TMS. Both are usually managed easily with over-the-counter analgesics. We will also give subjects a chance to experience the sensation of the frontal TMS for sub-study 3 via electric scalp stimulation, and they will have the opportunity to discontinue if they find the sensation unpleasant.

Subjects will be monitored continuously during TMS administration. In the event of a syncopal episode, all study procedures will be stopped. The subject will then be given first aid by the study staff, and evaluated by the LIP in charge.

As noted in Rossi et al. (2009), Loo and colleagues reported found mild and transient changes in auditory threshold in two depressed patients following a 2-4 week rTMS course of rTMS (Loo et al., 2001). Cases of tinnitus have been reported after rTMS treatments. In addition, recently in a study investigating the effects of rTMS on symptoms of depression, a patient experienced moderate to severe tinnitus after an rTMS session in which hearing protection was not used. Rossi et al. recommended that hearing protection always should be worn during rTMS application, and that individuals with cochlear implants not receive rTMS. Hearing protection will be worn by all subjects during rTMS procedures. Individuals with cochlear implants will be excluded from participation.

Risks to the unborn children of pregnant women receiving MRI and TMS are unknown. Pregnant women will be excluded as per CC policy.

MRI: The potential risks related to MRI will be minimized as follows: 1) Claustrophobia associated with MRI will be reduced by explaining the nature of the procedure in detail prior to subject enrollment; and 2) a possible history of any intraocular, intra-aural, intracranial, or intrathoracic metal will exclude the subject from the study. Earplugs will be given to each subject to wear during the scan to minimize discomfort and prevent any adverse effects on hearing resulting from the scanning procedure. Females of childbearing potential will undergo either serum or urine pregnancy testing to rule out pregnancy no more than 24 hours prior to each MRI session before the scanning procedures are initiated. A radiology technologist (or trained individual authorized to run the scanner) and a clinician will be present throughout the MRI study in case medical emergencies would arise. During MRI scanning, the subject can communicate with the control room personnel via an intercom at the operating console. Thus, the subject can be removed immediately from the MRI scanner, if necessary.

8. Subject Safety Monitoring

Subjects will be informed that they can withdraw from the study whenever they wish. Sample shocks will be administered prior to the study. At this point, subjects will be explicitly asked if they wish to continue. Subjects receiving the frontal TMS will also be given a chance to experience the sensation of the TMS via electric scalp stimulation. Subjects will be given the opportunity to discontinue after this sensation screen. The experiment will also be stopped for any subject who exhibits signs of distress during any phase of the study. Subjects will be constantly monitored via closed circuit video by the AI for MRI sessions. An AI is present during TMS sessions. A credentialed staff member (RN, NP or MD) will assess the subject at the conclusion of the study or at any time if significant side effects develop. The subject will be withdrawn at any time if unable to follow the rules for participation in this study.

9. Outcome Measures

a. Primary outcome measures

The primary outcome measures will be APS reduction as a function of stimulation type, active or sham stimulation.

10. Statistical Analysis

a. Analysis of data/ study outcomes

Sternberg. APS scores will be created by subtracting the startle magnitude during the safe blocks from the startle magnitude during the threat blocks. These scores will be analyzed using a 2 [block: active vs. sham] x 2 [stimulation: TMS vs. no TMS] x 2 [interval: maintenance vs. ITI] repeated measures ANOVA.

NPU. APS scores for the cue and ITI will be created by subtracting the startle magnitude during the safe blocks from the startle magnitude during the unpredictable blocks. FPS scores will be calculated by subtracting the startle magnitude during the predictable ITI from the startle magnitude from the predictable cue. These scores (APS cue, APS ITI, FPS cue) will be analyzed using a 2 [block: active vs. sham] x 2 [stimulation: TMS vs. no TMS] repeated measures ANOVA.

b. Power analysis

In our Sternberg pilot experiment, we obtained the effect size ($f=0.72$) for our observed WM load-related decrease in anxiety. Assuming a somewhat smaller effect size ($f=0.5$) due to regression to the mean, if we set power at .95 and experiment-wise, two-tailed alpha at 0.05. Based on these parameters, we will need 48 subjects per experiment. Assuming a 15% unusable data rate and 3 subjects to initially adjust the experimental procedure, we will need 58 subjects per experiment.

11. Human Subjects Protection

a. Subject selection

This study will be conducted in healthy males and females between the ages of 18-50. Participants will be recruited without any preference based on gender, race, religion, or other social variables. We have attempted to make our subject selection as equitable as possible.

Justification for exclusion of children

We want to test this paradigm in adults first to examine the scientific questions in the non-developing brain. If the findings are according to hypotheses, we would consider examining these questions in the pediatric population.

Justification for inclusion of other vulnerable subjects

This study will include only healthy volunteers.

Justification for exclusion of other vulnerable subjects

All subjects must be able to provide their own consent. This study is above minimal risk and we do not want to enroll participants who do not understand the risk/benefit ratio of the study, particularly when there is no benefit to the participants.

For this reason we exclude people with IQ lower than 80, or otherwise deemed to lack capacity to consent.

Protections for employees and staff participating in this study include 1) assuring that the participation or refusal to participate will have no effect, either beneficial or adverse, on the subject's employment or position at the NIH, 2) giving employees and staff who are interested in participating the "NIH Information Sheet on Employee Research Participation" prior to obtaining consent, and 3) assuring that there will be no direct solicitation of employees or staff. This study collects sensitive information (e.g. drug and alcohol use, specific medical diagnoses). The PI will train study staff regarding obtaining and handling potentially sensitive and private information about co-workers through staff discussions and written branch/section procedures. Information about sensitive information (e.g. drug and alcohol use, specific medical diagnoses) will be in the participant's NIH medical record.

Justification for exclusion of non-English speaking subjects

We exclude non-English speakers since not all the instruments and test we use are translated and validated in Spanish or other languages.

Justification for exclusion of subjects over 50 years of aged

As people get older, their startle response decreases (Le Duc et al., 2016). The upper age limit will be 50 years old to minimize the confounding effects of age.

Justification for exclusion of non-right-handed subjects

We have chosen to exclude individuals who are not right-handed because our hypothesis is based on pilot data showing lateralized patterns of activity in the prefrontal cortex. Given that our pilot data was recorded in right-handed individuals, it is unclear whether the results generalize to non-right-handed individuals.

Justification for exclusion of subjects with a history of drug or alcohol abuse or dependence

We will exclude subjects with a lifetime history of drug or alcohol dependence or abuse in order to select participants whose CNS physiology will not be confounded by changes induced by substance use.

Justification for exclusion of NIMH staff

We will exclude NIMH employees and staff to prevent bias from previous or current professional relations.

Justification for exclusion of pregnant or breast-feeding women

We exclude and rule out pregnant women via a pregnancy test because of the unknown effects of the shocks and of the fMRI on the developing fetus.

Justification for sensitive procedures

Electric shocks are used as the stressor in this study. Our use of electric shocks stems from our experience that electric shocks are among the most efficient ways to induce anxiety in the laboratory setting. Because of this advantage along with the fact that such

shocks have been very well tolerated by 100's of past participants in our psychophysiology experiments, we decided to again use electric shocks in our neuroimaging investigations described herein. TMS will be used to stimulate the dlPFC. According to our previous research, this should reduce anxiety potentiated startle. We chose TMS because it allows us to stimulate the dlPFC online, during the task, which is not possible with other methods like tDCS.

Safeguards for vulnerable populations and sensitive procedures

We assess pregnancy via urine test within 24 hours of any MRI session and exclude all participants who are pregnant. Neither participation nor refusal to participate as a subject will have an effect, either beneficial or adverse, on the participant's employment or position at NIH. The NIH Information Sheet on Employee Research Participation will be available to employees considering enrollment. All staff administering sensitive procedures will be trained and competency to administer procedures verified by the PI or AI.

b. Qualifications of investigators

